11.3 Records Retention

It is the investigator's responsibility to retain study essential documents for a minimum period of 7 years following completion of the study per UW-Madison institutional policy.

11.4 Publication and Data Sharing Policies

This study will be conducted in accordance with the following publication and data sharing policies and regulations:

This trial will be registered at ClinicalTrials.gov, and results information from this trial will be submitted to ClinicalTrials.gov. In addition, every attempt will be made to publish results in peer-reviewed journals.

12.0 STUDY ANALYSIS

12.1 Statistical Hypotheses

12.1.1 Primary Efficacy Endpoint(s):

Patients who receive local anesthetic via PIFB will demonstrate lower total opioid use during the initial 72 hours postoperatively compared to patients in the sham-control group.

12.1.2 Secondary Efficacy Endpoint(s):

- Patients who receive local anesthetic via PIFB will have a decreased intraoperative opioid requirement compared to patients in the saline-control group.
- Patients who receive local anesthetic via PIFB will have lower maximum and mean pain scores during the first 72 hours postoperatively and at 90 days postoperatively compared to patients in the saline-control group.
- Patients who receive local anesthetic via PIFB will demonstrate lower daily opioid use during the initial 72 hours postoperatively compared to patients in the sham-control group.
- Patients who receive local anesthetic via PIFB will demonstrate a significant reduction in time to extubation compared to patients in the saline-control group.
- Patients who receive local anesthetic via PIFB will demonstrate a significantly decreased time to return of bowel function compared to patients in the saline-control group.
- Patients who receive local anesthetic via PIFB will demonstrate a significantly reduced rate of postoperative delirium compared to patients in the saline-control group.
- Patients who receive local anesthetic via PIFB will demonstrate a significantly decreased ICU length of stay compared to patients in the saline-control group.
- Patients who receive local anesthetic via PIFB will demonstrate a significantly decreased hospital length of stay compared to patients in the saline-control group.
- Patients who receive local anesthetic via PIFB will demonstrate a significantly decreased persistent use of opioids at 90 days postoperatively compared to patients in the saline-control group.

12.2 Sample Size Justification

We conducted a retrospective chart review on prior single valve and CABG procedures utilizing a median sternotomy over a two-month period at our institution to characterize opioid consumption in our current patients. We found the average total opioid consumption in the first 72 hours following sternotomy was 245

MME (morphine milligram equivalents) +/- 87mg. We concluded that a 25% reduction in postoperative opioid requirements would be clinically significant, which is in line with what prior studies have utilized²⁷. Therefore, using a type 1 error rate of 0.05, power of 90%, and a sampling ratio of 1:1 between study arms, we calculated a sample size of 86 patients (43 patients per group). To compensate for potential dropouts and incomplete data, a total of 100 patients (50 patients in each group) will be targeted for enrollment.

12.3 Subject Population(s) for Analysis

- Intention-to-Treat (ITT): all randomized subjects
- Safety Analysis Dataset: all randomized subjects who received the required study intervention.
- Protocol-compliant Population: all randomized subjects who received the required study intervention.

12.4 Statistical Methods

The primary endpoint is total postoperative opioid requirement within 72 hours. Total opioid requirement will be measured in morphine equivalents, presented as mean +/- standard deviation, and compared between study groups using a two-tailed independent samples t-test. Secondary outcomes (total intraoperative opioid requirement, mean and maximum 72-hour postoperative pain scores, and pain score 90 days postoperatively) will also be presented as mean +/- standard deviation and compared using independent samples t-tests. Daily postoperative opioid use and mean pain scores on POD1, POD2, and POD3 will also be compared separately with Holm-Bonferroni correction. For pain scores, we will compare mean VRS and average each patient's score within each day before averaging across days. We recognize the debate in the literature about how to analyze pain scores. In the previously referenced randomized controlled trials^{19,20}, the authors used mean scores so we will do so as well.

Continuous secondary outcomes that we expect will not be approximately normally distributed (duration of mechanical ventilation, time until return of bowel function, ICU length of stay, hospital length of stay) will be presented as median with interquartile range and compared using Mann-Whitney tests. Categorical variables (delirium, chronic opioid use) will be presented as counts or as percentages and will be compared using Fisher's exact test. For all planned comparisons with parametric tests, non-parametric equivalents will be substituted if the assumptions of parametric testing are found to be violated before testing.

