8.0 SUBJECT SELECTION

8.1 Inclusion Criteria

Each patient must meet all of the following inclusion criteria to be enrolled in the study.

1. The patient provides consent to participate in study.
2. The patient is 18-80 years old.
3. The patient's ideal body weight (IBW) is >50kg.
4. The patient is planned to undergo coronary artery bypass graft or single valve repair/replacement surgery via median sternotomy.
5. The patient is undergoing an elective procedure.

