9.2 Method for Assigning to Treatment Groups

After consent is obtained, participants will be randomized to an intervention group. Randomization will be accomplished using an online service (www.randomizer.org) and prefilling sealed envelopes determining each subject's intervention group. Randomization will occur immediately prior to the intervention. All subjects will receive the standard of anesthesia care appropriate for their surgery or procedure as determined by the primary anesthesia team caring for the subject, regardless of randomization group. Each study subject as well as the OR anesthesia team, cardiac surgery team, cardiothoracic ICU team, and nursing staff caring for the patient will be blinded to the study drug the patient received. However, the anesthesia provider performing the block (separate from the provider caring for the patient in the operating room) will not be blinded to the study drug injected and will have access to all monitors deemed appropriate by the primary team caring for the subject. In order to maintain blinding during the procedure, the medication syringe will be covered by a towel after being drawn up and during injection to prevent the intraoperative teams from visualizing the contents being injected. The ultrasound will also be turned such that only the anesthesiologist performing the procedure can see, as Exparel has a distinct sonographic appearance on injection. Specific individuals who were involved in the block placement will not perform any follow-up assessments or evaluations of the study patients for the remainder of the study.

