10.0 STUDY CALENDAR, MEASUREMENTS, AND ACTIVITIES

10.1 Study Calendar

	Screening Visit 1 Phone/ inperson visit	Procedure Visit 2	ICU Visit 3	24- hours Post-op Visit 4	48-hours Post-Op Visit 5	72-hours Post-op Visit 6	3 Months or 90 days after DOS (Phone)
Window	Up to 60 days before surgery	Morning of Surgery	Followi ng surgical proced ure	24 hours post-op +/- 6 hours	48 hours post-op +/- 6 hours	72 hours post-op +/- 6 hours	
Screening	X						
Eligibility	X	X					

Informed Consent	X	X					
Demographics	X						
Medical History	SOC						
Randomization and Intervention: Pecto- Intercostal Fascial Plane Blocks vs Sham (control)		X					
Electronic Data Collection (EDC)		X	X	X	X	X	
Brief Pain Inventory Form							X
Concomitant Medications ¹		SOC	X	X	X	X	X
Adverse Events		SOC		SOC			

¹ All medications taken for analgesia at home regularly, prior to arrival on the day of surgery, and perioperatively (until 72 hours postoperatively) will be recorded.

². EDC will all capture the opioid intake, pain measurement and all other relevant study information that is not capture during the study procedures.

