10.2 Study Measurements

10.2.1 Preoperative Period - Screening (Visit 1)

- Age
- Sex
- Height
- Weight
- Body mass index
- Date of surgery
- Procedure
- Indication for procedure
- Baseline creatinine

- Baseline INR
- Baseline platelet count
- Preoperative anticoagulation
- Baseline left ventricle ejection fraction
- Baseline qualitative right ventricular function
- Presence of cirrhosis or end-stage liver disease diagnosis
- Presence of preoperative opioid use
- Baseline pain score (Numeric rating scale [NRS])

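### Section 12.4 compares 72-hour opioid use and pain with unadjusted t-tests although age, procedure and baseline pain are collected; a pre-specified ANCOVA is an optional, cheap and probably small gain

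*Combined protocol and SAP*

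**What the plan says.** Section 12.4 names total 72-hour MME as the primary endpoint, to be "compared between study groups using a two-tailed independent samples t-test". Total intraoperative opioid, "mean and maximum 72-hour postoperative pain scores, and pain score 90 days postoperatively" are also compared with independent samples t-tests. Daily opioid use and mean pain on POD1 to POD3 are compared separately with Holm-Bonferroni correction, but no test is named for them. The fallback is that "non-parametric equivalents will be substituted if the assumptions of parametric testing are found to be violated before testing". It is unadjusted too, as are the methods in the synopsis (section 3.1).

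Section 10.2.1 lists age, procedure and a baseline NRS pain score among the screening measurements. Section 8.1 admits two kinds of operation: "The patient is planned to undergo coronary artery bypass graft or single valve repair/replacement surgery via median sternotomy". On allocation, section 9.2 says "Randomization will be accomplished using an online service (www.randomizer.org) and prefilling sealed envelopes" and states no stratification.

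Section 12.2 takes its mean of 245 MME and SD of 87 from the site's own records: "We conducted a retrospective chart review on prior single valve and CABG procedures utilizing a median sternotomy".

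**The concern.** The SD of 87 MME includes whatever variation age, type of operation and baseline pain explain. A t-test leaves that part in the standard error, whereas a linear model that includes these variables removes it. The model estimates the same mean difference the trial was sized for and needs no new data. With about 100 patients and no stated stratification, naming the covariates in advance also prevents a post hoc choice if the arms differ by chance.

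What is at stake is some precision on the primary and pain endpoints. The validity of the comparison is not in question.

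**Working it through.** **Inputs.** From section 12.2: mean 245, SD 87, a 25% reduction, type 1 error 0.05, power 90%, 1:1 allocation, 43 evaluable and 50 enrolled per arm. From section 12.4: two-sided testing. R², the share of within-arm variance explained by the covariates, is not given; 0, 0.05, 0.10 and 0.20 are assumed.

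**The plan's own figure.** Difference = 0.25 × 245 = 61.25 MME, and 61.25 / 87 = 0.704 SD. Then n per arm = 2 × (1.960 + 1.282)² / 0.704² = 42.4, rounded up to 43, or 86 in total. This matches. By the noncentral t distribution, t-test power is 89.7% at 43 per arm and 93.6% at 50.

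**ANCOVA on MME, near-normal data.** With k covariates and n per arm:

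- SE = 87 × √[(2/n) × (1 − R²) × (2n − 3)/(2n − 3 − k)]
- df = 2n − 2 − k
- The factor (2n − 3)/(2n − 3 − k) charges for chance imbalance in the covariates. The t-test is the case k = 0, R² = 0.

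At 43 per arm the t-test SE is 87 × √(2/43) = 18.76, so the 95% CI half-width is 1.989 × 18.76 = 37.3 MME. With k = 3 and R² = 0, SE = 18.76 × √(83/80) = 19.11, and the half-width is 1.990 × 19.11 = 38.0 MME.

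| | t-test | R² = 0 | 0.05 | 0.10 | 0.20 |
|---|---|---|---|---|---|
| Power, 43 per arm | 89.7% | 88.6% | 90.1% | 91.6% | 94.3% |
| Power, 50 per arm | 93.6% | 92.9% | 94.1% | 95.1% | 97.0% |
| CI half-width, 43 per arm (MME) | 37.3 | 38.0 | 37.1 | 36.1 | 34.0 |

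The R² at which the two intervals are equally wide is 1 − (37.312/38.026)² = 0.037 at 43 per arm. The same calculation gives 0.032 at 50 per arm.

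**Is that R² plausible?** For procedure alone, R² = p(1 − p) × difference² / 87². Assume 50% to 70% have CABG. A CABG-valve difference of 30 MME gives 0.5 × 0.5 × 900 / 7569 = 0.030 down to 0.7 × 0.3 × 900 / 7569 = 0.025, below break-even. A difference of 45 MME gives 0.067 to 0.056, above it. The documents do not say which is nearer.

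**Pain, one covariate (k = 1), 43 per arm.** The CI is 0.6% wider at R² = 0, and 1.9%, 4.5% and 10% narrower at 0.05, 0.10 and 0.20. Break-even is about 0.012.

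**With the rank fallback kept.** Section 12.4 names no trigger, so a Shapiro-Wilk test at 0.05 in each arm is assumed.

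- Normal data, 43 per arm, 10,000 simulated trials per setting: ANCOVA/Mann-Whitney minus t/Mann-Whitney is -0.7, +0.3, +1.6 and +4.2 points at the four R² values.
- Lognormal data with mean 245 and SD 87, outcome shape held fixed, 43 per arm, 5,000 trials per setting: the fallback fires in 83-85% of trials, and the difference is -0.2, 0.0, 0.0 and +0.6 points.

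**The case against.** The strongest objection is that this is a preference. The t-test is unbiased under randomisation, no stated stratification factor calls for adjustment, and power at full enrolment is already 93.6%. The benefit rests on an R² the documents do not supply, and there are reasons to expect a low one:

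- The baseline NRS may be taken "Up to 60 days before surgery" (section 10.1).
- Current opioid users are excluded (section 8.2).
- 90-day pain comes from the Brief Pain Inventory, not the screening NRS (section 10.2.7).

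All of this stands. It sets the weight of the point but does not remove it, because the possible loss is small and the change is nearly free.

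A second objection also stands: opioid totals may well be skewed, and then the unadjusted rank test usually replaces the ANCOVA, leaving almost nothing to gain. A simulation that adds covariate effects to a skewed residual would suggest more, up to +1.9 points at R² = 0.20. In that set-up the outcome becomes less skewed as R² rises and the fallback fires less often, so it does not show what adjustment gains for a given outcome distribution.

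**Conclusion.** Optional improvement. Under near-normal MME at 43 per arm, it is worth between -1.1 and +4.6 power points over R² of 0 to 0.20 (88.6 − 89.7 and 94.3 − 89.7), and a CI from 2% wider to 9% narrower. At 50 per arm the range is -0.7 to +3.4 points. Under the lognormal assumption with the fallback kept, it is worth about -0.2 to +0.6 points. These figures rest on the assumed R² values and, for the fallback, on an assumed trigger.

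A reader might infer three stronger things that the documents do not support:

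- **That the planned test is wrong, biased or underpowered.** The sample size reproduces. The SD of 87 comes from a chart review that pooled valve and CABG cases, so the planned standard error already covers that case mix.
- **That adjustment always narrows the interval.** It does so only above the break-even R²; at R² = 0 the half-width widens from 37.3 to 38.0 MME.
- **That every pain comparison is a t-test.** Section 12.4 names that test for the 72-hour and 90-day scores, but names none for the daily ones.

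**What to change.** Fix the following in section 12.4 before unblinding:

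1. Total 0-72 h MME is compared by a linear model (ordinary model-based standard errors) on arm, age in years (linear), planned procedure (CABG or valve) and baseline NRS (linear).
2. The 72-hour mean and maximum pain scores, and 90-day pain, are compared by a linear model on arm and baseline NRS. One Brief Pain Inventory item is named as the 90-day score.
3. The daily POD1 to POD3 opioid comparisons use the MME model and the daily pain comparisons use the pain model, with Holm-Bonferroni kept. Total intraoperative opioid stays on the t-test, and the text says so.
4. A missing baseline NRS is replaced by the mean of the observed baseline values of both arms together. Section 12.5 only points to general guidance, so the rule has to be written down.
5. The non-parametric fallback stays, and the assumptions that trigger it are checked on the model residuals.
6. The adjusted mean difference is reported with its 95% CI, and the unadjusted t-test is a sensitivity analysis.

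The cost is SAP wording and a few lines of code, three degrees of freedom for MME and one for pain, and about one power point for MME if no covariate is prognostic. No new data are needed and the sample size stays as planned.

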Statistical Methodology	
Data analysis will be performed on an intent-to-treat basis based upon assignment to a study arm. Continuous data will be compared using student T-test or Wilcoxon-rank sum testing as appropriate. Categorical data will be compared using Chi-square or Fisher exact testing as appropriate. The data will be presented graphically where possible using scatter plots, profile plots, or histograms. For all tests, statistical significance will be defined as a p-value less than 0.05.

Estimated Subject Duration	
The duration of the study for each subject is approximately 100 days.

Estimated Enrollment Period & Study Duration	
Study enrollment and follow-up will occur over 3 months with the total expected duration of the trial to be 24 months.

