5.2 Rationale

Thousands of heart surgeries are performed every day in the United States²⁵. Unattenuated perioperative pain has been shown to contribute to increased morbidity, mortality, length of stay, and healthcare costs. Practice guidelines from the American Society of Regional Anesthesiologists recommend pre-incision techniques to reduce perioperative pain²⁶, however in cardiac surgery, there are no commonly used techniques to follow this recommendation. The PIFB is a newly described fascial plane block and existing literature supports the safety and efficacy of the PIFB in cardiac surgery patients. However, there are no randomized controlled trials evaluating this technique with a long-acting depot local anesthetic.

The purpose of this study is to determine whether bilateral pecto-intercostal fascial plane blocks with liposomal bupivacaine decrease pain and opioid requirements in patients undergoing cardiac surgery via median sternotomy compared to controls (sham blocks with saline). Our primary hypothesis is that patients receiving effective regional anesthesia with liposomal bupivacaine via PIFB will demonstrate a clinically significant (25%) reduction in total daily opioid consumption through 72 hours postoperatively compared to patients receiving standard of care without effective regional anesthesia (saline only via PIFB).

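### Does an unspecified switch from t-test to rank test, with no planned between-arm difference or confidence interval, weaken the primary analysis of 72-hour opioid use?

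*Combined protocol and SAP*

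**What the plan says.** For the primary endpoint, section 12.4 plans arm means with SDs, "compared between study groups using a two-tailed independent samples t-test". The section closes with a sentence covering every planned parametric comparison, and so the primary too: "non-parametric equivalents will be substituted if the assumptions of parametric testing are found to be violated before testing". It does not name the diagnostic, the cut-off or the person who decides. Section 12.4 also lists the continuous outcomes expected not to be normal (ventilation time, bowel function, ICU stay and hospital stay). The primary is not on that list.

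The synopsis (3.1) is looser: "Continuous data will be compared using student T-test or Wilcoxon-rank sum testing as appropriate". It adds the decision rule: "For all tests, statistical significance will be defined as a p-value less than 0.05".

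The size of effect appears in three places:

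- Section 12.1.1 asks only whether treated patients "will demonstrate lower total opioid use during the initial 72 hours postoperatively".
- Section 12.2 sizes the trial on a benchmark: "We concluded that a 25% reduction in postoperative opioid requirements would be clinically significant".
- Section 5.2 puts that benchmark in the primary hypothesis, as a "clinically significant (25%) reduction in total daily opioid consumption through 72 hours postoperatively".

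No section names a between-arm difference, a percentage reduction or a confidence interval as a result to be reported.

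**The concern.** Two things look wrong.

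First, a data-dependent choice between two primary tests, with no stated check, leaves room for discretion and can change the question. The t-test compares means, which is what the sample size rests on. The Mann-Whitney test compares distributions and is not tied to the mean difference.

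Second, the trial calls 25% clinically significant, yet its only stated criterion is a p-value below 0.05. Reductions well short of 25% can meet that. If the p-value were all that was reported, a reader could not tell a 15% effect from a 25% one. At stake is how the main result is interpreted.

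**Working it through.** **Inputs.** Section 12.2 gives a control mean of 245 MME, SD 87, a 25% reduction, and the design settings "using a type 1 error rate of 0.05, power of 90%, and a sampling ratio of 1:1 between study arms". It gives 43 per arm for analysis and 50 per arm enrolled. Section 12.4 makes the test two-sided. The documents give one SD and no distributional shape, so every shape below is an assumption.

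**1. The plan's own sample size.** The target difference is 0.25 × 245 = 61.25 MME, and 61.25/87 = 0.704 SD. The normal-approximation formula gives n = 2 × (1.960 + 1.282)² / 0.704² = 42.4, so 43 per arm and 86 in total, as stated. Exact t-test power is 89.7% at 43 per arm and 93.6% at 50.

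**2. Smallest significant difference.** This is t(0.975, 2n−2) × 87 × √(2/n).

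- n = 50: 1.984 × 17.40 = 34.5 MME, or 34.5/245 = 14.1%.
- n = 43: 1.989 × 18.76 = 37.3 MME, or 15.2%.

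A true 15% reduction would reach p < 0.05 in 55% of trials at 50 per arm and 49% at 43. So the p-value alone does not answer the 25% question. This is a general property of the design: with 90% power at two-sided 0.05, the smallest significant effect is about 1.96/3.24 = 60% of the target. Here it is 37.3/61.25 = 61% at 43 per arm.

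**3. What the planned summaries already give.** The percentage reduction is (control mean − active mean)/control mean. The interval for the difference needs only the two means, the two SDs and the numbers, all of which follow from the plan. For an observed 61.25 MME with SD 87 in both arms:

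- n = 50: 61.25 ± 34.5 = 26.7 to 95.8 MME.
- n = 43: 61.25 ± 37.3 = 23.9 to 98.6 MME.

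As a percentage of the control mean, with that mean's own error included, SE = √[(s₂/245)²/n + 0.75² × (87/245)²/n], where s₂ is the SD in the active arm. At n = 50 the interval is 12.5% to 37.5% if s₂ = 87, or 14.4% to 35.6% if s₂ = 0.75 × 87 = 65.25.

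**4. What the switching rule does.** The plan names no check, so the simulation assumed one: use Mann-Whitney if Shapiro-Wilk p < 0.05 in either arm. There were 10,000 trials per row. The Monte Carlo standard error at a 5% rate is √(0.05 × 0.95/10,000) = 0.002.

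| Assumed data | Per arm | Switch rate | t-test rejects | Plan's rule rejects |
|---|---|---|---|---|
| Normal, no effect | 50 | 0.094 | 0.0476 | 0.0480 |
| Log-normal, no effect | 50 | 0.893 | 0.0491 | 0.0516 |
| Normal, mean lower by 61.25 | 43 | 0.101 | 0.8940 | 0.8929 |
| Log-normal, scaled by 0.75 | 43 | 0.847 | 0.9623 | 0.9628 |
| Log-normal, shifted by 61.25 | 43 | 0.848 | 0.8912 | 0.9335 |
| Log-normal, both means 245, SDs 87 and 150 | 50 | 0.990 | 0.0525 | 0.1894 |

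The first two rows show type I error near 5%. Even an analyst who broke the rule and took the smaller of the two p-values would reach only 5.6% (normal) or 6.5% (log-normal).

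The next three rows show power equal to the t-test within Monte Carlo error, or about 4 points higher. At 50 per arm with SD 87 in both arms, separate runs gave 0.978 for the rule against 0.926 for the t-test (log-normal), and 0.950 against 0.933 (gamma).

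The size of the estimate barely depends on the route. The rank-based Hodges-Lehmann shift averages 56 to 63 MME against a true mean difference of 61.

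**The case for a change.** The strongest point is the last row of the table. With equal means but very different spread, the rank test rejects 19% of the time because the distributions do differ, although the means do not. A reader interested in mean opioid use would be misled, and nothing in section 12.4 excludes that case. This stands as a theoretical limit. It needs an SD 150/87 = 1.7 times as large in one arm with no shift in the mean, and nothing in the documents points to such a pattern. The planned arm means would also still be on the page, showing no difference.

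A second point is that results which can be derived are not results that are planned, and a rank p-value does not correspond to a mean difference. That is also true, but the arm means and SDs are planned for the primary endpoint whichever test is used, so the comparison with 25% remains available.

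A third point is that choosing before testing limits p-value shopping without defining the check or stating that it is blinded. That is a gap in detail, and the 5.6% to 6.5% worst case in step 4 bounds its effect on type I error when the arms share one distribution.

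Fixing the t-test has a price of its own: it gives up the extra power shown above for skewed data with equal SDs.

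**Conclusion.** The concern describes the text correctly but does not call for a change. The t-test is valid, is the named default and matches the sample size. Section 12.4 is the specific statement of method, and the synopsis only summarises it. Followed as written, the plan gives sound inference: type I error of 4.8% to 5.2% when the arms share one distribution, and power no worse than a fixed t-test beyond about 1 point, with a gain of roughly 2 to 6 points for skewed data with equal SDs.

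Exempting the primary from the switch is therefore a trade-off with no clear gain. Naming the mean difference, its interval or the assumption check would fill in detail that any competent report of arm means and SDs makes available. The 25% figure sizes the trial and motivates the hypothesis, but no section makes it a threshold for success, so the p < 0.05 rule does not conflict with it.

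The switch rates depend heavily on the assumed check and shape. A skewness cut-off of 1 instead of Shapiro-Wilk gives switch rates from 1% (normal) to 74% (log-normal). The conclusion would weaken only if the arms had similar means and markedly different spread.
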